# 3. Study Objectives and Endpoints

OBJECTIVES	ENDPOINTS
Primary	
-To evaluate changes in PWV following a 12-week home-based aerobic and muscle strengthening exercise program	-Within participant change from pre- to post- intervention as measured by carotid-femoral pulse wave velocity (PWV)
Secondary	
To evaluate changes in FMD following a 12-week home-based aerobic and muscle strengthening exercise program	-Within participant change from pre- to post- intervention as measured by brachial artery flow mediated dilation (FMD)
-To evaluate changes in the modifiable components of the ASCVD risk score (total cholesterol, HDL cholesterol, triglycerides, and systolic blood pressure) following the 12-week home-based comprehensive exercise program	-Within participant change of total cholesterol, HDL cholesterol, triglycerides, and systolic blood pressure from pre- to post-intervention
-To evaluate changes in functional fitness	-Within participant change of functional fitness from pre- to post-intervention as measured by the Functional Fitness Test
-To estimate muscle strengthening exercise session adherence	-Proportion of planned exercise sessions in which a participant completes at least 50% of prescribed exercises
-To estimate adherence to the aerobic physical activity guidelines (150 minutes/week)	-Proportion of planned weeks a participant accumulates 150 minutes of moderate intensity activity per week
-To estimate tele-coaching adherence	-Proportion of planned coaching sessions in which a participant completes
-To estimate acceptability	-Likert scale ratings of quality of exercise equipment, educational materials, health coaching, study feedback and distance delivery format
-To estimate changes in anthropometrics	-Within participant changes of waist and hip circumference, and weight from pre- to post-intervention
-To estimate changes in ambulatory activity levels	-Within participant change in average daily steps taken within a week from pre- to post-intervention as measured via ActiGraph accelerometer
-To estimate changes in psychosocial behavior change measures	-Within participant change of questionnaire scores (SEE, BPNES, PSS, BREQ-3) from pre- to post-intervention
-To estimate changes in diet	-Within participant change of questionnaire score (Multifactor Screener in Observing Protein and Energy Nutrition (OPEN)) from pre- to post- intervention

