SPPB. The short performance physical battery (SPPB) is a series of functional mobility assessments which measure balance, lower extremity strength, and fitness. Developed by the National Institute of Aging, the SPPB has clinically useful implications of predicting physical decline in older adults. The full battery utilizes standardized scoring, for a minimum of 0 points, to a maximum of 12 points, and includes the following three subscales: 1.) **Balance**. Each participant will stand for 10 seconds with their feet together, 10 seconds with their feet placed semi-tandem, and a final 10 seconds with their feet fully tandem. Participants receive a score from 0-4, based on their ability to attempt each position. 2.) **Repeated chair stand**, measuring lower extremity strength. Participants will stand up and sit down five times as quickly as they can. Participants receive a score of 0-4, based on total duration it takes to complete five total repetitions. 3.) **Gait speed**. Each participant will walk to a line placed on the floor three meters away at their typical walking pace. Participants receive a score from 0-4, based on total duration of walking this distance. **When collected:** Baseline, final visit (~14 weeks).

Exercise adherence. Adherence to intervention exercises will be measured via detailed exercise logs. A participant needs to complete at least 50% of the prescribed exercises in a session to be considered adherent to the session. **When collected:** ongoing, logs will be completed throughout the intervention and submitted at the final visit. Additionally, we will be monitoring participant's Fitbit data via Fitabase over the course of the study to monitor total physical activity and minutes of strength training logged.

Health coaching adherence. Adherence to health coaching will be monitored by the health coach on a weekly basis. A health coaching will be considered complete if the participant attends and participates in the health coaching session. Health coaches will also record the modality in which the session was completed, as well as the duration of completed sessions in minutes. **When collected:** ongoing, health coaches will record in REDCap whether a health coaching session was completed or not following each scheduled session.

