#### 6.3 Exercise intervention

During the study period, participants will be instructed to complete the muscle strengthening exercise routine twice a week for 12 weeks during the intervention, and to monitor one's total steps and active minutes. Personalized aerobic activity goals will be set and monitored via health coaches on the research study team. Participants will be assigned a study coordinator/health coach who will work with each participant over the course of the intervention. Study coordinators/health coaches will schedule weekly telehealth meetings with the participants for the first five weeks of the intervention, following the fifth week participants will be given the choice to continue meeting with their study coordinator/health coach weekly or transition to a tapered telehealth session schedule where they will meet with their study coordinator/health coach again during week 8 and week 11. At these health coaching sessions, a semi-standardized template will be used. Study coordinators will check in to determine study progress, help set and monitor exercise goals, systematically evaluate for adverse events, and will work to build rapport and support the participants on their exercise adoption and maintenance journey. Study coordinators/health coaches will also be instructed to assess for volume/intensity/difficulty of each of the exercises. These

sessions are done over video so that the coordinator can build rapport with participants, and that participants can show or demonstrate issues with exercises or their form. Participants will have access to a study-specific website with resources related to exercise prescription and exercise components (strivecardio-study.lab.uiowa.edu).

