#### 7. Statistical Considerations

#### 7.1 Statistical Methods

The primary objective of this pilot study is to obtain preliminary evidence of changes in PWV with the comprehensive exercise program. A 1 m/sec decrease in PWV from pre- to post-intervention reflects a clinically relevant change as this has previously been shown to be associated with a 15% risk reduction in CVD events. In statistical terms, we are testing the null hypothesis  $H_0$ :  $\Delta_{Post-Pre} = 0$  versus the alternative hypothesis  $H_1$ :  $\Delta_{Post-Pre} \neq 0$ . Using a repeated measures design with 1 within subject factor (time: pre- and post-intervention), the design achieves 93% power to test for a time effect among 30 participants. We will recruit 33 participants to account for a potential 10% dropout rate to accommodate a final analytic sample size of 30. Power calculations are based on the following assumptions: standard deviation of 1.4, using an F test, 5% significance level, an autocorrelation of 0.5, and 15% drop out.

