#### Muscle Strengthening Exercise Session Adherence

Exercise session adherence will be defined as the proportion of planned exercise sessions in which a participant completes at least 50% of the prescribed exercises. The mean and associated 95% confidence interval will be reported.

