#### (If yes, continue)

Our Study is a home-based exercise study for women who have completed treatment for endometrial cancer. This study is a 12-week cardio and strengthening exercise regimen to be done at home. The goal of this study is to measure improvements in your blood vessels, including stiffness and responsiveness and how that relates to overall health. We will also measure overall fitness including strength, agility and flexibility. Our staff will teach you how to do these exercises. You would be asked to come to the University of Iowa campus twice as part of this study, once at the beginning and again approximately 3 months later. You would be compensated \$50 at each visit. All exercise and fitness tracking materials will be provided, including resistance bands, a kettlebell, and a Fitbit.

Right now for this study, we want to see if this program improves your cardiovascular health including the health and function of your blood vessels, so that we have the potential to roll this out to a larger population of endometrial cancer survivors. Your participation would help us determine that.

For research purposes, we will be measuring different aspects of your health and fitness at a pre-study assessment and again at a post-study assessment. At these assessments, we will be taking a blood draw to test for things like cholesterol and glucose. We will also conduct a carotid-femoral pulse wave velocity and brachial artery flow mediated dilation. Those are tests that measure artery health. Both are non-invasive and involve using ultrasound equipment to measure the time it takes for blood to travel through your body. The carotid-femoral pulse wave velocity will have a sensor on your neck and anther on your thigh. The brachial artery flow mediated dilation will have a sensor on your arm. The blood flow to your arm will be temporarily restricted using a cuff and then released. All of these tests will be conducted by a professional in the Clinical Research Unit which is located in this hospital. We will ask you to be fasted for these tests.

Once we finish at the CRU, we will run through a series of functional fitness tests. This is a set of nine low impact tests looking at your strength, flexibility, and agility. There's no running or heavy lifting.

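### Strength-adherence logs have one stated hand-in point, the final visit, so the exercise-level records of women who do not attend are at risk of loss

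*Protocol*

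**What the plan says.** Protocol Section 3 lists strength adherence as a secondary endpoint: "Proportion of planned exercise sessions in which a participant completes at least 50% of prescribed exercises". Section 7.2.3 repeats the definition and plans a mean with a 95% confidence interval.

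Section 6.1 names the instrument, "Adherence to intervention exercises will be measured via detailed exercise logs", and the timing: "logs will be completed throughout the intervention and submitted at the final visit". The telephone script in Appendix 13 tells candidates "You would be asked to come to the University of Iowa campus twice as part of this study", so no campus visit falls between baseline and the final one.

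Four other items bear on the point:
- Section 6.1 also has Fitbit data followed throughout, including strength-training minutes.
- Section 6.3 says "Study coordinators/health coaches will also be instructed to assess for volume/intensity/difficulty of each of the exercises". For what is written down, Section 6.1 says "health coaches will record in REDCap whether a health coaching session was completed or not following each scheduled session", plus the modality and duration of the session.
- The schedule of events in Section 6 marks adherence in every week and at the final visit, without naming a source.
- The sample logs in Appendices 1 and 2 hold a place for a QR code whose use is not stated.

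On losses, Section 7.1 says "We will recruit 33 participants to account for a potential 10% dropout rate to accommodate a final analytic sample size of 30".

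**The concern.** The endpoint needs to know, session by session, whether at least half of the prescribed exercises were done. Only the log holds that. With the final visit as its single stated hand-in, a woman who drops out and does not return may take with her the record of every session she completed.

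The other streams do not fill the gap. Strength minutes on a Fitbit cannot show whether 4 of the 8 exercises on the Appendix 1 log were done. Coaches look at each exercise, but the protocol has them record only the coaching session itself.

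The women most likely to be missing are those who stopped. A mean over returned logs would then describe women who came back, while the stated denominator is planned sessions. The pilot is meant to inform a larger grant application, and adherence among all who start is part of that evidence. A later analysis plan can decide how to treat a missing log, but it cannot supply what was in it.

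**Working it through.** **Inputs from the protocol**
- Planned strength sessions (Section 6.3): 2 per week x 12 weeks = 24.
- Recruitment and loss (Section 7.1): 33 recruited at 10% dropout. 33 x 0.90 = 29.7, which agrees with the stated 30, so about 3 women are lost. The same section also lists 15% among its power assumptions; 33 x 0.15 = 4.95, about 5.
- Strength compliance in the earlier ten women (Section 2): 75%. All ten were retained.

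**Assumptions (not in the protocol)**
- Women who complete average 75%.
- Women who leave adhere at 75% until they stop and do no sessions afterwards. The base case is stopping after week 5.

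**Value for a woman who stops after week w**

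Value = 0.75 x w/12: 12.5% for w = 2, 31.25% for w = 5, 50% for w = 8.

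**All-starter mean, 3 of 33 lost**

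| Stop after week | Calculation | All-starter mean | Reported if left out | Overstatement |
|---|---|---|---|---|
| 2 | (30 x 0.75 + 3 x 0.125)/33 | 69.3% | 75.0% | 5.7 points |
| 5 | (30 x 0.75 + 3 x 0.3125)/33 | 71.0% | 75.0% | 4.0 points |
| 8 | (30 x 0.75 + 3 x 0.50)/33 | 72.7% | 75.0% | 2.3 points |

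**Other numbers lost, stopping after week 5**
- None lost: no error.
- 1 lost: (32 x 0.75 + 0.3125)/33 = 73.7%, overstated by 1.3 points.
- 2 lost: (31 x 0.75 + 2 x 0.3125)/33 = 72.3%, overstated by 2.7 points.
- 5 lost: (28 x 0.75 + 5 x 0.3125)/33 = 68.4%, overstated by 6.6 points.

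**What an analysis could still do without the logs**

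If the stop week is known, the sessions after it count as zero in the planned-session denominator. For a stop after week 5, 14 of 24 sessions are known zeros and 10 are unknown, so each woman lies between 0 and 10/24 = 41.7%. With three such women:
- lower bound: 22.5/33 = 68.2%
- upper bound: (22.5 + 3 x 10/24)/33 = 72.0%

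The range is 3.8 points wide and contains the 71.0% of the base case. The 75.0% obtained by leaving the women out lies above all of it.

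**Direction of the error**

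A woman who stops after week w can score at most w/12. That is below 75% for any stop before week 9, since 9/12 = 75%. For such women, leaving them out must raise the mean if completers average 75%. For later stops, or for women who keep exercising and only miss the visit, the direction is an assumption.

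**The case against.** The case on the other side has four parts.

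**Loss is not certain.** Section 6.1 describes logs as ongoing, the schedule marks adherence weekly, the coach gives a midpoint progress report (Section 5.1), and the QR code may be an upload link. A reader might infer that a woman who misses the final visit necessarily yields no log-based value. The protocol does not support that: the sentence describes the routine hand-in, and nothing stops staff from asking her to mail or photograph her logs. What stands is that no such route is stated, so the loss is a risk left open.

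**Omission and zero are not the only options.** A reader might infer that the analysis must either drop these women or score them as zero. The planned-session denominator allows the bounds shown above, and dated Fitbit minutes might narrow them. This stands in full. It limits the damage, but a bound is not the value.

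**The size rests on assumptions.** The stop week and adherence before stopping are not given, and Section 2 does not say that its 75% used the half-of-exercises rule. A reader might go on to infer that the reported 95% interval covers badly. That would need a between-woman standard deviation, and the protocol gives none. If it were 15 to 25 points, the half-width at n = 30 would be 2.045 x SD/sqrt(30) = 5.6 to 9.3 points, so the 3.8-point bound would be narrower than the half-width. No coverage claim is made here.

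**Return logistics often sit in a manual of procedures.** True, but here the protocol itself fixes the hand-in point, and fixes it less well than it does for coaching attendance, which is recorded after each scheduled session.

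**Conclusion.** The point holds as a minor one. Section 6.1 names the log as the measure, gives one hand-in point and states no route for a woman who does not attend. The exercise-level data of about 3 of 33 women are at avoidable risk.

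Under the base-case assumptions, leaving them out overstates mean strength adherence by about 4 points. The excess is 2.3 to 5.7 points as the stop moves from week 8 to week 2, and zero if nobody is lost, as in the earlier ten women. Scoring sessions after a known stop as zero bounds the all-starter mean at 68.2% to 72.0% in the base case without recovering it.

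The effect is confined to one descriptive secondary endpoint in a pilot. Pulse wave velocity, flow mediated dilation and the blood results do not depend on the logs.

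**What to change.** In Section 6.1, replace hand-in at the final visit with collection during the study:
- Each week's log is uploaded or photographed, or it is reviewed and entered in REDCap at the existing coaching contact. On the tapered option, weeks 6 to 8 are covered at the week 8 session and weeks 9 to 11 at week 11. Remaining logs come at the final visit.
- Outstanding logs are requested at withdrawal or after a missed final visit.
- If the QR code is the upload route, say so and give the timing.
- All women who start stay in the planned-session denominator.

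**Cost.** One or two sentences in an amendment, one added form and slightly more work for participants and coaches. The Subject Data section of the monitoring plan wants case report forms approved by the principal investigator and statistician before activation, so the added form should go through them. If enrolment is under way, early and late participants will differ in how logs were collected. The reported adherence figure will probably be lower.

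**What remains at risk.** If contacts are the only route on the tapered option, some sessions can still be outstanding:
- at most 6 (three weeks x 2) if no tapered contact before leaving is missed
- 8 (weeks 9 to 12) if week 11 and the final visit are missed
- 14 (weeks 6 to 12) if week 8 is missed as well

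As the protocol stands, all 24 are at risk. Weekly upload would reduce this further.

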#### 6.2 Exercise Familiarization

During the baseline visit, the study team will help the participant set up and activate their Fitbit device and account. They will also be oriented towards the basic functions of the Fitbit, demonstrating how to track one's steps and sync with their phone app. During the first week of participant accelerometer wear, following completion of informed consent and described baseline measures, participants will be given an exercise orientation and instructional visit virtually instructed by their designated health coach. The purpose of this session is for the participants to learn the exercise components of the intervention and understand how to safely use the equipment provided to them during their baseline visit. The instructional visit includes going through each exercise of the intervention (see Table below) to learn the movement, learn the muscle groups involved, and to learn how to monitor themselves by tracking their progress via logs. Each participant will receive a recommended starting point for each exercise with respect to intensity and progressions/regressions. For example, a participant may be starting on a blue resistance band for biceps curls, but the squats may simply be body weight at this time. Table 2 outlines the exercises for the intervention.

Table 2. Series of exercises, with progressions and regressions to increase/decrease difficulty.								
Primary muscle group	Exercise	Progressions	Regressions					
Thighs (quadriceps, hamstrings)	Body weight squats	Add resistance band     Holding dumbbells	Chair squats     Shortened range of motion					
Calves (gastrocnemius, soleus)	Standing heel raises	

 Holding dumbbells

 Elevate ball of foot

	Shortened range of motion					
Chest (pectoralis major & minor)	Standing chest press	Increase band tension	Reduce band tension					
Back (trapezius, latissimus dorsii)	Seated banded row	

Standing row

Increase band tension

	

Reduce band tension

Shorten range of motion

					
Abdominals (rectus & transverus adbominus)	Static v-sit hold with feet on floor	

 Elevate feet

 Add rotation

 Add dumbbell

	Support with hands     Add lumbar support w/ towel					
Shoulders (deltoids)	Seated banded press	

Standing

Use dumbbells

	

Reduce band tension

Shorten range of motion

					
Biceps brachii	Seated banded curl	

Standing

Add tension to band

Use dumbbells

	

Reduce band tension

Shorten range of motion

					
Triceps brachii	Seated arm extension	
 
Increase band tension
 
	Reduce band tension					

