## 6. Study Procedures

All participants will be asked to meet with the research team in-person at the University of Iowa Physical Activity and Cancer Survivorship (PACS) Lab in room 127 Iowa Bioscience Innovation Facility (IBIF) in a fasted state. Participants will be asked to bring a snack/food that can be refrigerated/stored in the lab after physiologic procedures. During the in-person visit in the PACS lab, participants will complete informed

consent from the study coordinator. After which, they will be escorted to the University of Iowa Clinical Research Unit (CRU) located in General Hospital 2 Boyd Tower at the University of Iowa Health Care main campus. While at the CRU participants will undergo described cardiovascular measurements by a trained technician before being escorted to the PACS Lab to break their fast to consume their snack/food, and then complete remaining described study protocols, and baseline assessments. They will also receive an ActiGraph accelerometer to wear for a seven-day wear protocol and then charge the device at home. They will also receive a Fitbit device and will receive instruction on how to use. Each participant will be asked to repeat the wear protocol week 12 of the study. These specific measures are described below. After completion of study baseline measures, participants will undergo an instructional session to the exercise program described below in **section 6.2**.

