Accelerometer. Although participants will have a Fitbit for self-monitoring, we will use a research grade device to determine ambulatory activity levels at the beginning and end of the study. At the baseline visit, participants will be asked to wear the ActiGraph wGT3X-BT accelerometer (ActiGraph, Pensacola, FL) for 7 days during all waking hours. They will then be asked to keep the

device at home, charge it, and then will repeat this wear protocol on week 12 of the study. Participants will be instructed to notify (via call or email) the research staff once the baseline ActiGraph wear has been completed. ActiGraph is a gold standard method of objective activity assessment. In advance of the final week of the protocol participants will be asked to re-wear the ActiGraph device and bring the device and associated wear logs back to the final study visit. When collected: Baseline pre-intervention, last week of the intervention (~12 weeks)

Demographics and health history. At baseline, participants will be asked about sociodemographic factors, self-reported health history, cancer history will be abstracted from their medical records. In order to corroborate medical information for those coming from the lowa Cancer Registry, we will be requesting relevant medical records from the participant's local oncologist or medical provider. The request will be sent in HIPPA compliant manner using a fax machine only accessible by the Principal Investigator. These questions will be collected from/stored on our secure REDCap database. **When collected:** Baseline

Self-efficacy for exercise surveys. At baseline and at follow-up, participants will be asked to complete two versions of the self-efficacy for exercise (SEE) scale. This 9-item survey will ask about self-efficacy (or confidence) related to aerobic exercise and then about muscle strengthening exercise. We will administer these two surveys at baseline and then at the end of the study as modality-specific measures of self-efficacy. **When collected:** Baseline, final visit (~14 weeks)

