#### Ambulatory Activity Levels

The within patient change in average daily steps taken within a week will be assessed from pre- to post-intervention. Mixed effects regression models will be used to estimate changes in ambulatory activity levels. Random effects will be included to account for the longitudinally correlated nature of repeat measurements within a patient. Estimated mean and associated 95% confidence interval will be reported.

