At the end of the first assessment, you will be given exercise equipment and measurement tools. This includes resistance bands, an adjustable dumbbell, a Fitbit, and an accelerometer which is a pedometer that can also measure speed and distance. The first three will be for you to keep and the accelerometer we will need back at the end of the study. The Fitbit is for you to wear during the 12 weeks that you will be doing the exercises. We will get information from that Fitbit during that time. It comes straight to our account that we have set up for you. After the 12 weeks, you get to keep that Fitbit and we will turn over the account to you. We will not track your movement once the account goes to you. We will give you the login info and we recommend that you change it to whatever you would like.

Does all of that makes sense?

Now the final part of this study is weekly online coaching check-ins. We have a research assistant who will coordinate meeting times with you to see how you are doing. A change in routine like this can seem like a lot, so we want you to be able to have someone to discuss how things are going. If you like certain

exercises, or don't like others. If you have struggled with mastering an exercise, or if you made improvements and want to share the good news. That will be designated one-on-one time for you to discuss whatever aspects of the study you would like.

Do you have any questions about the study?

Does this sound like something you would be interested in doing?

(If no) Okay, thank you for your time. Have a great day!

(If yes) Great, I have a few eligibility questions I would like to discuss. (Go through eligibility questions)

(If they fail) I'm sorry, unfortunately you are not eligible for this study. I appreciate the time you took to speak with me today.

(If they pass, continue)

You are eligible, which is great!

What I would like to do know is to go over the highlights of the consent. This is not a contract. It simply details all the information you would need for the study. You won't be signing this today. We will go over the important information together so you have a clear understanding of what will be happening before you come in for your first assessment. We will have you sign the consent at your first assessment when a study member can go over it with you.

(Go over the consent)

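### The Fitbit is activated, with step-tracking instruction, at the visit that opens the baseline ActiGraph week, and Protocol sections 6 to 6.2 do not delay its use, so the secondary step change could be biased toward zero

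*Protocol*

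**What the plan says.** **The endpoint.** Section 3 lists a secondary objective, "To estimate changes in ambulatory activity levels", measured by ActiGraph. The analysis section adds: "The within patient change in average daily steps taken within a week will be assessed from pre- to post-intervention".

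**The baseline week.** Section 5.1 places one week of accelerometer wear before exercise begins. The accelerometer entry in section 6.1 gives the collection times as "Baseline pre-intervention, last week of the intervention (~12 weeks". It also says: "Participants will be instructed to notify (via call or email) the research staff once the baseline ActiGraph wear has been completed".

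**The Fitbit.** Section 6, describing the visit at which the ActiGraph is issued, says: "They will also receive a Fitbit device and will receive instruction on how to use". Section 6.2 says: "During the baseline visit, the study team will help the participant set up and activate their Fitbit device and account", and describes staff "demonstrating how to track one's steps and sync with their phone app". In the schedule of events, device orientation and the first ActiGraph entry share the Baseline column. Section 5.1 counts the Fitbit among the intervention's equipment, and section 6.1 describes it as a self-monitoring tool.

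**When the Fitbit is to be worn.** The clearest statement is in the Appendix 13 telephone script: "The Fitbit is for you to wear during the 12 weeks that you will be doing the exercises". That script is for registry recruits. Section 4 also recruits from the gynecologic oncology clinic.

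**The concern.** The Fitbit feeds back to the participant the same behaviour that the ActiGraph measures. Once it is activated and its step display explained, it is a working part of the intervention. The protocol puts it in participants' hands at the start of the week that is meant to record their activity before the intervention.

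If some of them start using it at once and walk more because of it, the baseline step count no longer describes their usual activity. The step change would then understate what the programme, Fitbit included, did to ambulatory activity. A control group given the devices on the same timetable could offset a baseline shift of this kind; this trial has a single arm.

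**Working it through.** The protocol gives no expected step change, standard deviation or power for steps, so there is no planned figure to reproduce. The check is one of timing and direction.

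**1. Order of events.**
- Baseline visit: ActiGraph issued, Fitbit issued and activated, step tracking and phone syncing shown (sections 6 and 6.2).
- Next seven days: ActiGraph worn for the baseline value (sections 5.1 and 6.1).
- End of that week: the participant notifies staff that wear is complete (section 6.1).
- Weeks 1 to 12: exercise, with ActiGraph wear repeated in week 12.

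The Fitbit is therefore available and working throughout the baseline week.

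**2. Text that would keep it out of use in that week.** Sections 6, 6.1 and 6.2 contain no instruction to leave the Fitbit off, hide its display or postpone wear. Three places point to use from Week 1: the Appendix 13 script; the Adherence row of the schedule, which starts at Week 1; and section 6.3, which puts step monitoring under the exercise intervention. Two places are looser: section 6.3 refers to the study period, and the exercise adherence entry in section 6.1 has Fitbit data monitored over the course of the study. The text leans toward later use but does not secure it.

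**3. Direction.** Let D be the mean step change that would be seen with an undisturbed baseline. Let p be the proportion of analysed participants who use the Fitbit in the baseline week, and r their mean resulting rise in daily steps in that week. Then

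observed change = mean(post) − [mean(undisturbed pre) + p × r] = D − p × r.

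If p = 0 or r = 0, there is no bias. If both are positive, the estimate is too low by p × r. For a true gain larger than p × r, that is a shift toward zero. A mixed model for two time points estimates the same mean difference and does not correct a shifted baseline by itself.

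**4. Size.** Neither p nor r is in the documents, and no value of either can be inferred from them.

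**5. What can be recovered.** Section 8.2.1 says Fitbit data stream continuously to the Fitbit servers and are pulled into Fitabase. Fitbit data dated in the baseline wear week would therefore show who wore the device then, which estimates p directly. The step change can be re-estimated without those participants.

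**6. Other endpoints.** PWV, FMD, blood markers and the fitness tests are taken at the visits themselves. The baseline values precede any Fitbit use at home, so this route does not touch them.

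**The case against.** The strongest reply is that the protocol nowhere says the Fitbit is worn in the baseline week. Appendix 13 describes only two campus visits, so equipment has to be issued at the first, and activating a device is logistics. The script's statement about the 12 exercise weeks describes the same single-arm study and is fair evidence of general intent, even though it is addressed to registry recruits. Pages between Appendix 9 and Appendix 13, the consent pages and the exercise manual were not available and may contain wear instructions. The endpoint is one of many secondary ones in a pilot, and the bias would shrink an apparent gain, not create one.

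Most of this stands. It rules out saying that the baseline is contaminated and keeps the point minor. What it does not answer is that the procedures themselves, as visible, activate a self-monitoring tool at the start of a week labelled pre-intervention and leave its non-use to inference. A recruitment script states intended use; it does not instruct staff or participants to leave an activated device alone.

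A reader might also infer that a contaminated baseline would be beyond repair. The documents do not support that: the Fitabase record allows exposed participants to be identified and a sensitivity estimate made. That repair is partial. Those excluded are not a random subset, and removing them from about 30 analysed participants costs precision.

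**Conclusion.** The point holds as a low-cost improvement to a data-collection procedure. The stated timing of Fitbit activation leaves the baseline ActiGraph week open to self-monitoring, and any resulting rise in steps would bias the secondary step change toward zero. This rests on three assumptions: that some participants use the device in that week, that the feedback raises their steps, and that no unseen page already prevents it. None can be confirmed from the documents.

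The size cannot be derived and may be zero. It would be tempting to attach a figure in steps per day or a percentage of the effect, but both inputs would be invented. It would also be wrong to extend the point to the primary endpoint: PWV, like FMD, is unaffected.

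**What to change.** In sections 6.1 and 6.2, state that the Fitbit account may be set up at the baseline visit, but that wearing the device and viewing its data begin only after the participant gives the notice section 6.1 already requires at the end of baseline ActiGraph wear. Apply this to clinic and registry recruits alike. It writes into the procedures what the Appendix 13 script already implies.

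For participants already enrolled, use Fitabase to count how many have Fitbit data dated within their baseline wear week. Report that count, and give a sensitivity estimate of the step change without them beside the main estimate. Take the count before study access ends: section 8.2.1 has the accounts deleted after study completion, while the script has them handed over to participants.

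The cost is one or two sentences in each section and a short remote contact, by video or telephone, to start the Fitbit after the baseline week. No new visit, device or measurement is needed.
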